2.3 Primary Endpoint

2.3.1 Kinome signature pathway will be based on comparison of kinome expression from pre- and post-treatment biopsies using Multiplexed Inhibitor Beads (MIBs) coupled with mass spectrometry

3.0 PATIENT ELIGIBILITY

3.1 Main Study Inclusion Criteria

Subject must meet all of the inclusion criteria to participate in this study:

- 3.1.1 Age ≥ 18 years
- 3.1.2 Signed written informed consent
- 3.1.3 Histologically confirmed V600E or V600K BRAF mutant melanoma
- 3.1.4 Unresectable Stage III/IV melanoma
- 3.1.5 ECOG PS 0-2
- 3.1.6 Normal organ function as defined by the following:
- Absolute neutrophil count $\geq 1.2 \times 10^9/L$
 - Hemoglobin ≥ 9 g/dL, platelets $\geq 75 \times 10^9/L$
 - PT/INR and PTT $\leq 1.5 \times$ ULN (Note: subjects receiving anticoagulation treatment may enroll with INR established within the therapeutic range prior to D1 of treatment)
 - Albumin ≥ 2.5 g/dL
 - Total bilirubin $\leq 1.5 \times$ ULN (patients with elevated bilirubin due to Gilbert's disease will not be excluded)
 - AST and ALT $\leq 2.5 \times$ ULN
 - CrCl ≥ 50 mL/min per Cockcroft-Gault
- 3.1.7 Prior anti-cancer treatment related toxicities except alopecia and lab values as outlined in section 3.1.6 must be \leq Grade 1 as per NCI CTCAEv4.
- 3.1.8 Willing to undergo biopsy for research purposes only (see section 6.6). **Note:** If possible, the pre-treatment biopsy should be performed after all other eligibility criteria are confirmed. Please also see the note in section 6.9.3 regarding assessment of biopsied lesions per RECIST v1.1.
- 3.1.9 Females of child-bearing potential: willing to use two forms of effective contraception, and to continue use for 16 weeks (4 months) post last dose of study medication. Effective contraception is defined as:
- An intrauterine device with a documented failure rate of less than 1% per year.
 - Male partner sterilization prior to the female subject's entry, and this male is the sole sexual partner for that female.
 - Complete abstinence from sexual intercourse for 14 days prior to enrollment, throughout study treatment, and for at least 4 months after the last dose of study treatment. Abstinence is only acceptable when in line with the preferred and usual lifestyle of the subject. Periodic abstinence (e.g. calendar, ovulation, symptothermal, post-ovulation methods, etc) and withdrawal are not acceptable methods of contraception.

- Double-barrier contraception: condom and occlusive cap (diaphragm or cervical/vault caps) with a vaginal spermicidal agent (foam/gel/cream/suppository).

Note: Hormonal-based methods (e.g., oral contraceptives) are not permitted as contraception due to potential drug-drug interactions with dabrafenib. Female subjects who are lactating must discontinue nursing prior to the first dose of study treatment and must refrain from nursing throughout the treatment period and for 4 months following the last dose of study treatment.

Females of non-childbearing potential are those who are postmenopausal (defined as greater than 1 year without menses with an appropriate clinical profile, e.g., age appropriate, >45 years in the absence of hormone-replacement therapy (HRT). In questionable cases, the subject must have a follicle-stimulating hormone (FSH) value >40 mIU/mL and an estradiol value <40 pg/mL (<140 pmol/L); or who have had a bilateral tubal ligation or tubal occlusion, bilateral oophorectomy or hysterectomy. Men with a female partner of childbearing potential must have either had a prior vasectomy or agree to use effective contraception as described from D1 of treatment, throughout the treatment period, and for 16 weeks after the last dose of study treatment. If a subject becomes pregnant during the treatment period of the study, the study treatments should be stopped immediately.

- 3.1.10** In women of child-bearing potential, negative serum pregnancy test within 48 hours prior to day 1 of study treatment and agree to use effective contraception as outlined in section 3.1.9
- 3.1.11** Measurable disease as defined by RECIST v1.1
- 3.1.12** Able to swallow and retain oral medication
- 3.1.13** Left ventricular ejection fraction by ECHO \geq institutional lower limit of normal
- Patients with a history of hypertension MUST have hypertension adequately controlled (BP < 140/90) with appropriate anti-hypertensive therapy or diet prior to study entry. Note:** To be eligible a subject must have an average of BP below 140/90 based on 3 separate measures. If the subject has a record of BP recordings taken at home, \leq 20% of BPs taken should have numbers > 140/90.

3.2 Main Study Exclusion Criteria

Any subject meeting any of the following exclusion criteria at baseline will be ineligible for study participation:

- 3.2.1** Patients with a history of a prior malignancy are excluded unless they have been disease free for 3 or more years or unless they have a completely resected non-melanoma skin cancer, and/or subjects with indolent second malignancies.

- 3.2.2** History of malignancy with confirmed activating RAS mutation at any time. *Note:* Prospective RAS testing is not required. However, if the results of previous RAS testing are known, they must be used in assessing eligibility
- 3.2.3** Prior treatment with a BRAF inhibitor (including but not limited to dabrafenib (GSK2118436), vemurafenib, and LX281/BMS-908662) or a MEK inhibitor (including but not limited to trametinib (GSK1120212), AZD6244, and RDEA119); **NOTE:** There is no limit to the number of other prior therapies, and patients may be previously untreated.
- 3.2.4** Have a known immediate or delayed hypersensitivity reaction or idiosyncrasy to drugs chemically related to study drug, or excipients or to dimethyl sulfoxide (DMSO).
- 3.2.5** Active GI or intracranial hemorrhage
- 3.2.6** History or evidence of cardiovascular risk including any of the following:
- QTc \geq 480 msec;
 - History or evidence of current clinically significant uncontrolled arrhythmias;
 - Exception: Subjects with controlled atrial fibrillation for >30 days prior to D1 of study treatment are eligible.
 - History of acute coronary syndromes (including myocardial infarction and unstable angina), coronary angioplasty, or stenting within 6 months prior to study entry;
 - Patients with history of hypertension **MUST** have hypertension adequately controlled (BP < 140/90) with appropriate anti-hypertensive therapy or diet **prior to study entry**
- Note:** To be eligible a subject must have an average of BP below < 140/90 based on 3 separate measures. If the subject has a record of BP recordings taken at home and in their medical record, \leq 20% of BPs taken should have numbers > 140/90.
- Patients with intra-cardiac defibrillators or permanent pacemakers;
 - Known cardiac metastases;
 - Abnormal cardiac valve morphology (\geq grade 2) documented by echocardiogram (subjects with grade 1 abnormalities [i.e., mild regurgitation/stenosis] can be entered on study). Subjects with moderate valvular thickening should not be entered on study.
- 3.2.7** History of known glucose-6-phosphate dehydrogenase (G6PD) deficiency

3.2.8 Brain metastases are excluded unless:

- All known lesions were previously treated with surgery or stereotactic surgery (whole-brain radiation is not allowed unless given after definitive treatment with surgery or stereotactic surgery), AND
- Brain lesion(s), if still present, must be confirmed stable (i.e., no increase in lesion size) for ≥ 12 weeks prior to D1 of study treatment (stability must be confirmed with two consecutive magnetic resonance image (MRI) or computed tomography (CT) scans with contrast, AND
- Asymptomatic with no corticosteroid requirements for ≥ 4 weeks prior to D1 of study treatment, AND
- Treatment with any CYP enzyme inducing anticonvulsants occurred < 4 weeks prior to D1 of study treatment

NOTE: if study subject has history of brain metastasis, but currently has no evidence of disease in brain (NED), confirmation by two consecutive scans separated by ≥ 6 weeks prior to D1 of treatment is required.

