3.2.9 Pulmonary embolism on active therapy

3.2.10 History of interstitial lung disease or pneumonitis

3.2.11 Known HIV, Hepatitis B or C infection (with the exception of chronic or cleared HBV and HCV infection, which will be allowed provided the following tests are done at screening: viral hepatitis serology, Hepatitis B surface antigen and Hepatitis B core antibody (IgM) and/or Hepatitis C RNA)

3.2.12 Currently active GI disease, or prior surgery that may affect ability to absorb oral medications

3.2.13 History or current evidence/risk of retinal vein occlusion (RVO) or retinal pigment epithelial detachment (RPED):

- Predisposing factors to RVO or RPED (e.g. uncontrolled glaucoma or ocular hypertension, uncontrolled systemic disease such as hypertension, diabetes mellitus, or history of hyperviscosity or hypercoagulability syndromes)
- Visible retinal pathology as assessed by ophthalmic exam that is considered a risk factor for RVO or RPED such as:
 - Evidence of new optic disc cupping
 - Evidence of new visual field defects
 - Intraocular pressure > 21 mm Hg

3.2.14 Currently receiving cancer therapy (chemotherapy, radiotherapy, immunotherapy, or biologic therapy) **NOTE:** palliative radiation therapy is permitted for non-target lesions that are either new or present at baseline provided total dose does not exceed 30 Gy; however, radiation skin injury has been reported with concurrent use of dabrafenib and radiation. See concomitant medications section 4.5.3 for recommendations when palliative radiation is prescribed.

3.2.15 Use of other prohibited medications within 5 half-lives or 14 days prior to the first dose of study drugs or requires any of these medications while receiving medication on this study (see section 4.5)

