4.5 Concomitant Medications/Treatments

4.5.1 Prohibited Medications, Herbal Supplements and Juices

The use of certain medications for 14 days or 5 half-lives prior to the first dose of study therapies and for the duration of the trial will not be allowed. If a prohibited medication is required for single use (such as for a procedure) while treatment with study drug is interrupted, the PI can approve such use. The following medications or non-drug therapies are prohibited:

- Other anti-cancer therapy while on treatment in this study
- Other investigational drugs
- The concurrent use of all herbal supplements is prohibited during the study (including but not limited to St. John’s wort, kava, ephedra (ma

huang), ginkgo biloba, dehydroepiandrosterone (DHEA), yohimbe, saw palmetto, or ginseng).

- Antiretroviral drugs. Subjects with known HIV are ineligible for study participation.
- Drugs that are clinically relevant strong inhibitors or inducers of CYP3A, CYP2C8, p-glycoprotein (Pgp) or breast cancer resistance protein (BCRP) transporter because they may alter dabrafenib and/or trametinib concentrations. These include but are not limited to those listed in section 11.2 (see Appendices); consider therapeutic substitutions for these medications. This list may be modified based on emerging data.

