5.2.6 Contraindications

Drugs that are strong inhibitors or inducers of CYP3A or CYP2C8, Pgp or BCRP transporters, are contraindicated. See appendices and sections 4.5 and 11.2.1. Any known hypersensitivity to the constituents of the vehicle would contraindicate dabrafenib use.

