¹¹Tumor imaging should remain consistent throughout study, and will include contrasted computed tomography (CT) scan of chest, abdomen and pelvis. These tests may be performed within 7 days prior to the study visit. At screening, a scan of the brain is required; MRI unless contraindicated, in which case a CT scan with contrast may be substituted. Beyond screening, a scan of the brain is not required but should be repeated if clinically indicated. For patients removed from treatment for reasons other than disease progression, follow-up tumor assessments (if available) should be documented until PD is confirmed.

¹² The frequency of tumor assessment scans reduced to every 12 weeks for subjects responding to combination therapy after cycle 9
AND
For subjects responding to combination therapy for > 2 years, reduce the frequency of disease assessment scans to every 6 months.

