11.2 Appendix B Prohibited Drugs, and Drugs to be used with Caution

11.2.1 PROHIBITED MEDICATIONS (also see section 4.5.1)

- Anti-retroviral drugs (e.g., ritonavir, saquinavir, atazanavir)
- All herbal supplements including but not limited to St. John's wort, kava, ephedra (ma huang), ginkgo biloba, dehydroepiandrosterone (DHEA), yohimbe, saw palmetto, or ginseng. Grapefruit juice must also be avoided.

OTHER PROHIBITED MEDICATIONS¹	
Strong CYP2C8/3A/Pgp/Bcrp Inhibitor/Inducer	Therapeutic Area
clarithromycin, telithromycin, rifamycin class agents (e.g. rifampin, rifabutin, rifapentine), troleandomycin	Antibiotics
itraconazole, ketoconazole, posaconazole, voriconazole	Antifungals
nefazodone	Antidepressants
gemfibrozil	Hyperlipidemia
carbamazepine, oxcarbamazepine, phenobarbital, amiodarone, phenytoin, s-mephenytoin, bosentan, mibefradil, modafinil, conivaptan, topiramate	Miscellaneous
pioglitazone, troglitazone	Antidiabetics
cyclosporine	Immunosuppressive agents
¹ This list may be modified based on emerging data.	

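### Exclusion 3.2.8: the anticonvulsant condition for admitting patients with treated brain metastases is worded backwards

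*Combined protocol and SAP*

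**What the plan says.** The lead-in to Section 3.2 makes each exclusion decisive on its own: "Any subject meeting any of the following exclusion criteria at baseline will be ineligible for study participation". Section 3.2.8 then excludes brain metastases unless four bulleted conditions hold, with AND between them. In substance they are:

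1. All known lesions were treated by surgery or stereotactic surgery.
2. Any lesion still present has been stable for at least 12 weeks.
3. "Asymptomatic with no corticosteroid requirements for ≥ 4 weeks prior to D1 of study treatment".
4. "Treatment with any CYP enzyme inducing anticonvulsants occurred < 4 weeks prior to D1 of study treatment".

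A note beneath the list concerns patients with a history of brain metastasis and no current evidence of it. It asks for two confirming scans and does not mention anticonvulsants.

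Elsewhere the protocol restricts enzyme inducers. Section 3.2.15 excludes "Use of other prohibited medications within 5 half-lives or 14 days prior to the first dose of study drugs". Section 4.5.1 sets a matching ban on a list of drugs, with its period given as "14 days or 5 half-lives prior to the first dose of study therapies and for the duration of the trial will not be allowed"; strong CYP3A and CYP2C8 inducers are on that list. Section 5.2.6 states: "Drugs that are strong inhibitors or inducers of CYP3A or CYP2C8, Pgp or BCRP transporters, are contraindicated". The prohibited list in Appendix B (11.2.1) includes "carbamazepine, oxcarbamazepine, phenobarbital, amiodarone, phenytoin, s-mephenytoin" and, further along the same row, topiramate.

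**The concern.** The fourth bullet is phrased as a reason to exclude, but it sits in a list of conditions for admission, so its effect is reversed. Followed literally, it turns away the patients the exception was written for: those with controlled brain disease and no recent exposure to an inducer.

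This is an operative eligibility rule. Footnote 11 to the Time and Events Table says "At screening, a scan of the brain is required", so the rule is reached whenever brain metastases are known or found at screening. Section 9.5.2 rules out eligibility exceptions for individual subjects, so a site cannot use a waiver to get round the wording. A site that reads the bullet as a washout is applying a criterion different from the approved one, and a site that reads it literally is excluding the wrong patients.

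**Working it through.** The plan gives no figure to reproduce on this point. The check is one of logic, followed by a small calculation of which patients can pass both relevant rules.

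**Step 1: the logic of 3.2.8.** Write the rule as: excluded unless (A and B and C and D), where A to C are the first three bullets and D is the fourth. Take a patient for whom A, B and C are true, and let L be the whole days from last inducer use to Day 1 (4 weeks = 28 days).

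| Exposure to an enzyme-inducing anticonvulsant | D as written | Result under 3.2.8 as written | Result under a 4-week washout |
|---|---|---|---|
| Never | False | Excluded | Admitted |
| Last use L ≥ 28 | False | Excluded | Admitted |
| Last use L < 28 | True | Admitted | Excluded |

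Every row comes out opposite to a washout.

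**Step 2: direction of the surrounding rules.** Bullet 3 requires at least 4 weeks *without* corticosteroids. Section 3.2.15 requires a period *without* prohibited drugs, 4.5.1 prohibits strong inducers before and during treatment, and 5.2.6 contraindicates them. Only bullet 4 asks for recent exposure.

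**Step 3: who passes both 3.2.8 as written and 3.2.15.** This applies to users of a drug on the prohibited list. Let h be the drug's half-life in days. The documents give no half-lives for these drugs, so h is assumed over a range. Reading the two periods in 3.2.15 as whichever is longer (also an assumption):

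- 3.2.8 bullet 4 as written needs L < 28.
- 3.2.15 bars L < max(14, 5h).
- Both are passed when max(14, 5h) ≤ L ≤ 27.

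| Assumed h (days) | 5h | Passing values of L | Number of days |
|---|---|---|---|
| up to 2.8 | up to 14 | 14 to 27 | 14 |
| 3 | 15 | 15 to 27 | 13 |
| 4 | 20 | 20 to 27 | 8 |
| 5 | 25 | 25 to 27 | 3 |
| 5.6 or more | 28 or more | none | 0 |

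**Step 4: sensitivity to the reading of 3.2.15.** If the 14-day period is taken to include day 14 itself, the first row becomes 15 to 27 (13 days). If the shorter period governs, the window is wider: at an assumed h of 1 day, 5h = 5 and L = 5 to 27 passes (23 days). For an inducer that is not on the prohibited list, 3.2.15 does not bite and the whole range L = 0 to 27 passes. Under every one of these readings, never-exposed patients and those with L ≥ 28 remain excluded by bullet 4.

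**The case against.** The strongest reply is that this is an obvious drafting slip. The protocol prohibits strong inducers, the steroid bullet points the right way, and staff would in practice apply a washout. Section 9.3 routes all registrations through one office, which limits divergent readings. The study is a 20-patient, single-arm comparison of tumour tissue before treatment and at progression, and its analysis does not turn on brain-metastasis patients. No patient is shown to have been wrongly turned away. All of that is fair and limits the consequences, but it does not change what the approved text requires.

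Four narrower points also deserve an answer:

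- **The note under 3.2.8.** It could be read as a separate route for patients with no current brain disease. It only asks for scan confirmation and nowhere waives the fourth bullet. Even on the generous reading, patients with residual stable lesions are still affected.
- **Scope of the prohibition.** The bullet covers any enzyme-inducing anticonvulsant, whereas 4.5.1, 5.2.6 and Appendix B bar strong inducers, and 4.5.2 allows mild or moderate ones with caution. This stands. The cross-references establish the intended direction, but they do not bar every drug the bullet covers.
- **The 14-to-27-day window.** It depends on the longer-of reading and on assumed half-lives. This also stands, and the window should be taken as approximate.
- **A misread symbol in the extracted text.** This is unlikely, since the inequality signs in the neighbouring bullets are intact. Even with the sign reversed, wording that requires treatment to have occurred would still exclude patients never exposed.

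**Conclusion.** The criterion is wrong as written and should be corrected. For patients with brain metastases who meet the first three conditions, it excludes those never exposed to an enzyme-inducing anticonvulsant and those off it for 4 weeks or more. That conclusion follows from the text alone.

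The reach is limited. The rule decides eligibility only within that subgroup, whose size the documents do not give, and how sites actually applied it is unknown. It does not permit on-study use of listed strong inducers, because 3.2.15 and 4.5.1 apply independently. The sample size and power in Section 8.1 are untouched.

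**What to change.** Replace the fourth bullet of 3.2.8 with: *No treatment with any CYP enzyme-inducing anticonvulsant for at least 4 weeks before Day 1.* This matches the form of the steroid bullet and covers never-exposed patients. Section 3.2.15 stays as it is and continues to apply alongside, including where 5 half-lives exceeds 4 weeks.

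Check the records of any brain-metastasis patients already screened or enrolled against the corrected criterion, and document which reading was applied.

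The cost is a one-line eligibility amendment through the IRB under Section 9.6, plus the record check, which is small in a 20-patient trial. No extra procedures are needed.

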3.2.9 Pulmonary embolism on active therapy

3.2.10 History of interstitial lung disease or pneumonitis

3.2.11 Known HIV, Hepatitis B or C infection (with the exception of chronic or cleared HBV and HCV infection, which will be allowed provided the following tests are done at screening: viral hepatitis serology, Hepatitis B surface antigen and Hepatitis B core antibody (IgM) and/or Hepatitis C RNA)

3.2.12 Currently active GI disease, or prior surgery that may affect ability to absorb oral medications

3.2.13 History or current evidence/risk of retinal vein occlusion (RVO) or retinal pigment epithelial detachment (RPED):

- Predisposing factors to RVO or RPED (e.g. uncontrolled glaucoma or ocular hypertension, uncontrolled systemic disease such as hypertension, diabetes mellitus, or history of hyperviscosity or hypercoagulability syndromes)
- Visible retinal pathology as assessed by ophthalmic exam that is considered a risk factor for RVO or RPED such as:
 - Evidence of new optic disc cupping
 - Evidence of new visual field defects
 - Intraocular pressure > 21 mm Hg

3.2.14 Currently receiving cancer therapy (chemotherapy, radiotherapy, immunotherapy, or biologic therapy) **NOTE:** palliative radiation therapy is permitted for non-target lesions that are either new or present at baseline provided total dose does not exceed 30 Gy; however, radiation skin injury has been reported with concurrent use of dabrafenib and radiation. See concomitant medications section 4.5.3 for recommendations when palliative radiation is prescribed.

3.2.15 Use of other prohibited medications within 5 half-lives or 14 days prior to the first dose of study drugs or requires any of these medications while receiving medication on this study (see section 4.5)

3.2.16 Pregnant or lactating female

3.3 Inclusion Criteria for Off-Study Subjects to Receive Progression Biopsy

3.3.1 Currently progressing on Trametinib/Dabrafenib Combination Therapy

3.3.2 Willing to undergo biopsy for research purposes only.

[figure not shown]
3.3.3 Tumor amenable to research biopsy.

3.3.4 Signed written informed consent to have a progression biopsy performed on the LCCC 1128 protocol.

3.3.5 Previously enrolled on the LCCC 1128 study and did not have a progression biopsy previously performed while on study.

4.0 TREATMENT PLAN

4.1 Schema

^aPatient must have tumor accessible to biopsy to be eligible if frozen tissue from diagnostic specimen is not available.

^bPatient may remain on treatment after progression if evidence of continuing clinical benefit

^cClinical or radiological

^dReasons may include, but are not limited to, inability to tolerate the combination of dabrafenib and trametinib, receiving other therapy, or completion of 3-years of study treatment without progression

^eThe subject may be placed back on the combination trametinib/dabrafenib therapy as part of his/her standard of care treatment plan

^fThe subject may have a progression biopsy taken after progression on standard of care treatment if the subject is eligible and consents to this biopsy. Progression can be defined clinically or radiologically.

This is an open label study of patients with unresectable stage III and stage IV melanoma with mutant V 600E/K melanoma and tumor that is accessible to biopsy. Patients can have had any number of prior lines of treatment (and may be previously untreated), but may not have previously received either a BRAF or MEK inhibitor for treatment of their melanoma.

Patients will receive the BRAF inhibitor dabrafenib and MEK inhibitor trametinib orally at the RP2D determined in the Phase I/II study (BRF113220): trametinib 2mg QD and dabrafenib 150 mg BID on a continuous basis. A cycle will be defined as 3 weeks in duration. Cycles will be repeated until disease progression (clinical or radiological). Patients may remain on treatment after progression (at the discretion of the investigator) as long as they are still experiencing clinical benefit. Patients will be requested to remain on study medication until the biopsy at progression is performed.

Patients will have a biopsy at baseline and at progression. Some subjects may be removed from study prior to progression for other reasons that include, but are not limited to, an inability to tolerate the combination of dabrafenib and trametinib, a need to receive other therapy, or completion of 3-years of study treatment without progression. If one of these subjects later receives the combination of dabrafenib and trametinib per his/her standard of care treatment plan, then the subject may re-consented for a biopsy upon progression. These subjects are required to consent to re-enter the study for the purposes of having a progression biopsy.

KinominingTM and NextGen Sequencing (in patients who co-enroll into LCCC1108) will be done on baseline and progression biopsies to look for changes in kinome expression and mutations in resistance genes.

